14. PUBLICATION POLICY

The results of this study may be published in a medical publication, journal, or may be presented at a medical conference or used for teaching purposes. Additionally, this study and its results may be submitted for inclusion in all appropriate health authority study registries, as well as publication on health authority study registry websites, as required by local health authority regulations. Selection of first authorship will be based on several considerations, including, but not limited to study participation, contribution to the protocol development, and analysis and input into the manuscript, related abstracts, and presentations in a study.

[figure not shown]
[figure not shown]

16. APPENDICES

16.1. Severity of Alopecia Tool (SALT)

Olsen/Canfield

Left Quadrant Raw Score (LRS)		Top Quadrant Raw Score (TRS)	
Right Quadrant Raw Score (RRS)		Back Quadrant Raw Score (BRS)	
Total SALT Score $[(LRS \times 0.18) + (RRS \times 0.18) + (TRS \times 0.40) + (BRS \times 0.24)]$			

16.2. Patient Satisfaction Questions

16.2.1. Satisfaction of Hair Coverage Question

How satisfied are you with the hair coverage on your scalp today?

- 0 Very dissatisfied
- 1 Dissatisfied
- 2 Somewhat satisfied
- 3 Mostly satisfied
- 4 Very satisfied

16.2.2. Satisfaction of Hair Coverage Quality Questions

For the next set of questions, please choose the best answer that represents how you feel today.

1. How satisfied are you with the thickness of the hair coverage on your scalp?	 1 Very dissatisfied	 2 Dissatisfied	 3 Somewhat satisfied	 4 Mostly satisfied	 5 Very satisfied
2. How satisfied are you with the evenness of the hair coverage on your scalp?	 1 Very dissatisfied	 2 Dissatisfied	 3 Somewhat satisfied	 4 Mostly satisfied	 5 Very satisfied
3. How satisfied are you with the thickness of the individual hairs on your scalp?	 1 Very dissatisfied	 2 Dissatisfied	 3 Somewhat satisfied	 4 Mostly satisfied	 5 Very satisfied
4. How satisfied are you with the texture/feel (coarseness, softness etc.) of the individual hairs on your scalp?	 1 Very dissatisfied	 2 Dissatisfied	 3 Somewhat satisfied	 4 Mostly satisfied	 5 Very satisfied
5. How satisfied are you with the current color of the hair on your scalp?	 1 Very dissatisfied	 2 Dissatisfied	 3 Somewhat satisfied	 4 Mostly satisfied	 5 Very satisfied
6. How satisfied are you with your eyebrows?	 1 Very dissatisfied	 2 Dissatisfied	 3 Somewhat satisfied	 4 Mostly satisfied	 5 Very satisfied
7. How satisfied are you with your eyelashes?	 1 Very dissatisfied	 2 Dissatisfied	 3 Somewhat satisfied	 4 Mostly satisfied	 5 Very satisfied

16.3. Patient Visual Analog Scale (VAS) for Eyebrows

At this time, please describe your eyebrows by placing a mark on the line.

## **LIST OF ABBREVIATIONS**

Abbreviation or Specialist Term	Explanation
AE	Adverse event
ATC	Anatomical-Therapeutic-Chemical
BID	Twice daily dosing
CI	Confidence interval
CSR	Clinical study report
CTCAE	Common terminology criteria for adverse events
ECG	Electrocardiogram
eCRF	Electronic case report form
HDL	High-density lipoprotein
ICH	International Conference on Harmonisation
LOCF	Last Observation Carried Forward
MedDRA	Medical Dictionary for Regulatory Activities
QD	Once daily dosing
QT	QT interval
QTcF	QT interval corrected for heart rate (Fridericia's method)
SAE	Serious Adverse Event
SALT	Severity of Alopecia Tool
SAP	Statistical Analysis Plan
SD	Standard deviation
SI	International System of Units
SOC	System organ class
TEAE	Treatment-emergent adverse events
VAS	Visual Analog Scale
WHO	World Health Organization

## **1. PURPOSE OF THE STATISTICAL ANALYSIS PLAN**

This statistical analysis plan (SAP) contains detailed information to aid in the implementation of the statistical analyses and reporting of the study data for use in the clinical study report (CSR) for study CP543.2002. This SAP is being written with due consideration of the recommendations outlined in the most recent International Conference on Harmonisation (ICH) E9 Guideline, entitled Guidance for Industry: Statistical Principles for Clinical Trials, and the most recent ICH E3 Guideline, entitled Guidance for Industry: Structure and Content of Clinical Study Reports.

This SAP describes the data sets that will be used for analysis, as well as patient characteristics, efficacy, safety, and clinician-reported and patient-reported perception of disease severity and improvement parameters. The details of the specific statistical methods stated in the protocol will be provided and any changes from the protocol-specified analyses will be documented in the SAP prior to database lock. If additional analyses are required to supplement the planned analyses described in this SAP after the database lock, they may be completed and will be described in the CSR. Table, figure, and listing specifications are provided as an attachment in a separate document. This SAP is based on the latest version of the protocol (Amendment 1), dated 03 January 2019.

## **2. PROTOCOL SUMMARY**

### **2.1 Study Objectives**

The overall objective of the study is to compare the efficacy and tolerability of a 16 mg total daily dose of CTP-543 utilizing two different dosing regimens in adult patients with chronic, moderate to severe alopecia areata.

The secondary/exploratory objectives of the study will be to assess the patient reported outcomes of hair coverage and hair coverage quality.

### **2.2 Study Design**

This is a randomized, parallel group multicenter study to evaluate the efficacy and tolerability of two dosing regimens of CTP-543 (8 mg twice daily dosing (BID) vs 16 mg once daily dosing (QD)), in adult patients with chronic, moderate to severe alopecia areata. Patients will be between 18 and 65 years of age and experiencing an episode of alopecia areata lasting at least 6 months and not exceeding 10 years, with at least 50% hair loss as measured by the Severity of Alopecia Tool (SALT) at Screening and Baseline, and are not concurrently being treated for alopecia areata with other treatments that might affect hair regrowth or immune response. Up to approximately 75% of alopecia areata patients with alopecia totalis or universalis, and no more than 10% with only alopecia ophiasis will be enrolled.

Patients may be screened up to 28-days prior to initiation of study drug. The Treatment Period is a 24-week dosing period where patients will be randomized to receive either CTP-543 8 mg BID, or CTP-543 16 mg QD and will be analyzed for the primary endpoints of the study. To minimize bias in the evaluation of study endpoints, patients, investigators, and site personnel will be unaware of the active drug dosing regimen by administering one 16 mg tablet and one placebo tablet 12 hours apart from each other for the 16 mg QD study group.

Patients will take the first dose of study drug in the clinic on Day 1. Patients will be instructed to take study drug every 12 hours. Patients should dose study drug in the clinic on all Study Visit Days after clinical laboratory blood draws are completed.

Patient safety will be monitored throughout the trial. The patient will be tested to ensure they do not have the Hepatitis B or C virus, thyroid function abnormalities or latent or active Tuberculosis, during the screening period. During the first 8 weeks of the Treatment Period, hematology and serum chemistry will be conducted every 2 weeks, followed by an assessment every 4 weeks thereafter through completion of the study at 24 weeks. Lipid levels will be assessed every 12 weeks throughout the Treatment Period. Significant cytopenias or other hematologic abnormalities will be managed by severity through dose interruption, or discontinuation, and signs and symptoms of infection will be closely monitored and treated promptly. Patients who experience intolerable symptoms during treatment may discontinue the study at the discretion of the Investigator. Patients may withdraw consent at any time. The Treatment Period will last 24 weeks to assess BID and QD doses, in parallel. Assessment of treatment response with SALT for efficacy will occur at 4, 8, 12, 16, 20 and 24 weeks. Upon completion of the 24-week Treatment Period patients will be eligible to either complete

treatment and exit the study following the safety follow-up visit, or roll-over into a long-term open-label extension study.

Approximately 60 patients are planned to be enrolled in the study; approximately 30 patients per dosing regimen.

### **2.3 Study Population**

The study population will consist of male and female patients of any ethnicity between 18 and 65 years of age, inclusive, with diagnosis of alopecia areata with a current episode lasting at least 6 months and not exceeding 10 years at the time of Screening. Total disease duration greater than 10 years is permitted. Patients must also exhibit at least 50% scalp hair loss, as defined by a SALT  $\geq 50$ , at Screening and Baseline.

A full list of the inclusion and exclusion criteria can be found in Sections 7.1 and 7.2 in the CP543.2002 Protocol.

### **2.4 Treatment Regimens**

CTP-543 will be dosed orally as tablets. Doses and frequency will be allocated as follows:

- CTP-543 8 mg BID (every 12 hours)
- CTP-543 16 mg QD (16 mg in the morning and placebo tablet in the evenings)

### **2.5 Treatment Group Assignments or Randomization**

Patients meeting all inclusion criteria and none of the exclusion criteria will be randomized to CTP-543 8 mg BID or CTP-543 16 mg QD in a 1:1 ratio. Randomization will be stratified by classification of alopecia areata subtype into one of the following three categories: 1) alopecia areata, 2) alopecia totalis or alopecia universalis, or 3) alopecia ophiasis.

### **2.6 Sample Size Determination**

A sample size of 25 patients (completers) per group provides adequate precision for the estimated dosing regimen difference for relative change in SALT score from baseline at Week 24. Precision of the estimated difference is quantified by the width of the 90% confidence interval (CI) for the dosing regimen difference.

### **3. GENERAL ANALYSIS AND REPORTING CONVENTIONS**

The following is a list of general analysis and reporting conventions to be applied to this study, unless otherwise specified.

All data displays (tables, listings, and figures) will have a header showing the sponsor company name, protocol number, page number, and display status (i.e. “DRAFT” or “FINAL”), as well as a footer indicating file name and run date/time. Summary tables and data listings will be summarized by dosing regimen and overall, as appropriate. All data collected per-protocol and all derived variables will be listed.

Categorical variables will be summarized using counts (n) and percentages (%) and will be presented in the form “n (xx.x).” If a count is 0, 0% will be shown for the percentage. If a percentage is 100%, 100% will be shown with no decimal place. To ensure completeness, summaries for categorical variables will include all categories, even if no patients had a response in a particular category. Unless otherwise specified, the denominator for each percentage will be based on the number of patients in the population being summarized (header n). If missing values are present, counts will be shown but will not be included in percentage calculations.

Continuous variables will be summarized using mean, standard deviation (SD), minimum, maximum, median, and number of patients. The mean and median will be reported to an additional level of precision than the original observations, and the SD will be reported to two additional levels of precision than the original observations. The minimum and maximum will be the same precision as the original data. In general, any calculated values, such as those due to unit conversion, will be rounded to the same number of decimal places as the original data.

Confidence intervals will be 90%. No formal hypothesis tests will be performed. Testing will be performed only for the Treatment Period. Estimates and confidence intervals may be reported to 1 more decimal than the original data.

Summary tables and data listings:

- No preliminary rounding will be performed; rounding will only occur after analysis.
- Data from patients excluded from an analysis population will be presented in the data listings but will not be included in the calculation of summary statistics, where applicable.
- Data from each patient will be separated by a blank line. Within a data listing, if a descriptive item appears line after line (e.g., repetition of a patient number, date, visit, etc.), only the first occurrence will be displayed (e.g., in Listing of Vital Signs, patient number, date and visit will only be displayed on first row when presenting all parameters collected at same visit). Repetition of actual results or outcomes (e.g., Adverse Events (AEs), lab results, vital sign values, etc.) will not be collapsed.
- Data listings will be sorted by dosing regimen, patient, and week and/or time of assessment, as applicable.

- When change from baseline or change to baseline is calculated, baseline is the last observation obtained prior to dosing of the study drug.

Mock tables and data listings will be provided as attachments to this analysis plan. Minor changes to the mocks after formal SAP approval will not necessitate re-approval unless changes to the text of the SAP are required.

All statistical deliverables will be produced, validated, and reviewed for accuracy/consistency in accordance with [REDACTED] standard operating procedures and the processes described in the statistical validation plan.

SAS® (SAS Institute, Cary, North Carolina) statistical software, version 9.4 or later, will be used for all analyses. Adverse Events and Medical History will be coded in Medical Dictionary for Regulatory Activities (MedDRA) Version 19.1. Concomitant medications will be coded in World Health Organization (WHO) Drug Version E (2016.01) and Anatomical-Therapeutic-Chemical (ATC) classification and preferred term.

## **4. ANALYSIS POPULATIONS**

Analysis populations will be summarized and listed for each patient, by dosing regimen.

### **4.1 Efficacy Population**

The Efficacy Population will include all patients who receive study drug and have at least 1 post-treatment SALT assessment during the Treatment Period. Patients in the Efficacy Population will be analyzed according to their randomized dosing regimen.

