11.3. Analysis Populations

The Efficacy Population will include all patients who receive study drug and have at least 1 post-treatment SALT assessment. The Safety Population will include all patients who receive study drug. Patients will be summarized according to study drug regimen received (i.e., as treated) should it differ from the randomized arm.

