## **8.4 Overview of Efficacy Analysis Issues**

### **8.4.1 Handling of Dropouts or Missing Data**

The Last Observation Carried Forward (LOCF) approach will be implemented for missing SALT score data, e.g., if the SALT score in the Week 16 visit window is missing, the next and closest available on-treatment SALT score measurement before the Week 16 visit window will be used for all remaining SALT assessments: Week 16, Week 20 and Week 24. Missing baseline values will not be carried forward. If a SALT assessment is missing between two non-missing SALT

assessments visits, the SALT score at that visit will be interpolated using the mean of the closest pre- and post-assessments.

If the number of discontinuations due to adverse events is substantial, other methods will be explored.

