### **8.5 Analysis Methods**

No formal hypothesis tests will be conducted. All confidence intervals will be 90%. Testing will be based on the Efficacy Population and performed only for the Treatment Period.

[Table 8-1](#) gives an overview of the analysis methods that will be used for each of the efficacy variables.

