### **8.5.2 Secondary Efficacy Analyses**

Descriptive statistics and 90% confidence intervals will be reported for the SALT score (observed values, relative change, and absolute change) at each time point for each dosing regimen and by subtype. By-patient data listing will also be presented for patient SALT scores. The mean of observed value, absolute change, and relative change SALT scores along with 90% confidence intervals for each dosing regimen will be presented using line graphs.

Responders at 90%, 75%, and 50% by visit will be summarized with proportions and 90% confidence intervals (using the binomial approximation with a Wald continuity correction). Responders are defined as patients with at least 90%, 75%, or 50% reduction in SALT score by visit. Percent reduction is calculated as the baseline SALT score minus the current value, divided by the baseline value, multiplied by 100. Responders will be presented graphically by dosing regimen as a bar graph at 24 Weeks and as a line graph across time.

Responses to the patient satisfaction question will be summarized with proportions and 90% confidence intervals (using the binomial approximation with a Wald continuity correction). Responses will be also categorized as “Satisfied” (including responses of “Very satisfied,” “Mostly satisfied,” and “Somewhat satisfied”) and “Dissatisfied” (including responses of “Very dissatisfied” and “Dissatisfied”) and presented as a 2 x 2 shift table from baseline to Week 24. Response will also be listed in the by-patient data listings.

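### Responder rates leave out dosed patients who have no post-baseline SALT at all, instead of counting them as non-responders

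*SAP*

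**What the plan says.** The two documents agree on who is analysed for efficacy. SAP 4.1: "The Efficacy Population will include all patients who receive study drug and have at least 1 post-treatment SALT assessment during the Treatment Period". Protocol 11.3 has the same restriction: "The Efficacy Population will include all patients who receive study drug and have at least 1 post-treatment SALT assessment". SAP 4.1 adds that these patients are analysed by randomised regimen.

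SAP 8.5 applies this population to efficacy: "Testing will be based on the Efficacy Population and performed only for the Treatment Period". The planned lists in SAP 14 and 15 confirm it for tables 14.2.2.2 (90/75/50% responders) and 14.2.3.4 (SALT ≤10/20/25) and for responder figures 14.2.1.2 and 14.2.1.3.

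SAP 3 makes the header count of the population being summarised the default denominator for percentages, and adds: "If missing values are present, counts will be shown but will not be included in percentage calculations".

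SAP 8.5.2 defines response without a rule for patients who have no data: "Responders are defined as patients with at least 90%, 75%, or 50% reduction in SALT score by visit". SAP 8.4.1 deals with gaps as follows: "The Last Observation Carried Forward (LOCF) approach will be implemented for missing SALT score data". It draws on earlier on-treatment scores and interpolates between visits. SAP 12 adds no responder analysis on all randomised or all dosed patients.

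**The concern.** Membership of the Efficacy Population depends on something that happens after randomisation, namely having a SALT while on study. SALT is not scheduled at Week 2, so a patient who leaves before Week 4 without an Early Termination SALT is removed. LOCF cannot restore that patient because there is no on-treatment score to carry. Protocol 7.3 lists loss to follow-up as a reason for withdrawal, allows withdrawal at any time, and does not replace those who leave.

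For a responder endpoint, a dosed patient who never shows a response is ordinarily a non-response. Dropping the patient shrinks the denominator and leaves the numerator alone, so the arm's rate can only stay the same or rise. The study compares the efficacy and tolerability of two regimens. If one regimen lost more patients very early, its response rate would be raised more by this rule.

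**Working it through.** **Inputs**
- Dosed patients per arm: 30 (Protocol 6.3 and SAP 2.2, approximate).
- Reference response: 47% with at least a 50% reduction at 8 mg BID in study CP543.2001 (Protocol 4.2.1). Used for illustration only.
- Patients per arm with no post-baseline SALT, k: not given. The working assumption is 0 to 2. Values up to 5 are shown because going from 30 enrolled to 25 completers (SAP 2.6) leaves room for 5 losses in total, so k = 5 is the extreme in which all of them occur before any SALT.
- Interval for a difference in proportions: 90% Wald with continuity correction (1/n₁ + 1/n₂)/2 (Protocol 11.4.2).

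**Step 1: the reference rate.** 0.47 × 30 = 14.1, taken as 14 responders; 14/30 = 46.7%, close to the quoted 47%.

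**Step 2: one arm's rate.** As planned: 14/(30 − k). With the excluded patients counted as non-responders: 14/30 for every k.

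| k | As planned | Counted as non-responders | Gap (points) |
|---|---|---|---|
| 0 | 14/30 = 46.7% | 46.7% | 0 |
| 1 | 14/29 = 48.3% | 46.7% | +1.6 |
| 2 | 14/28 = 50.0% | 46.7% | +3.3 |
| 3 | 14/27 = 51.9% | 46.7% | +5.2 |
| 4 | 14/26 = 53.8% | 46.7% | +7.2 |
| 5 | 14/25 = 56.0% | 46.7% | +9.3 |

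**Step 3: the regimen difference.** Take 14 responders in each arm, so the difference on all dosed patients is 0. The half-width is 1.645 × √[p₁(1 − p₁)/n₁ + p₂(1 − p₂)/n₂] + (1/n₁ + 1/n₂)/2.

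- All 30 counted in both arms: 1.645 × √(2 × 0.467 × 0.533/30) + 1/30 = 0.212 + 0.033 = 0.245. Difference 0, 90% CI −24.5 to 24.5 points.
- One arm loses 1: difference +1.6, CI −23.2 to 26.4.
- One arm loses 2: difference +3.3, CI −21.7 to 28.4.
- One arm loses 5: difference +9.3, CI −16.5 to 35.2.
- Both arms lose the same k: a zero difference stays zero. A non-zero difference is multiplied by 30/(30 − k), which is 30/28 = 1.07 at k = 2.

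**Step 4: which rule removes these patients.** It is the population definition. The SAP 3 rule on missing values is not the cause, because these patients are already outside the header count. It would matter after a change of population: if they were admitted and still treated as missing, that rule would take them out of the percentage again.

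**The case against.** Several points on the other side stand.

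- **The group is narrow.** Protocol 7.3.1 asks that anyone who stops early have all Week 24 assessments, which include SALT, at an Early Termination Visit. A patient who attends stays in the population. A reader might infer that all early dropouts vanish from the response rates, but the documents do not support that. Only those with neither a Week 4 or later SALT nor an Early Termination SALT are lost. Still, patients lost to follow-up or withdrawing consent are the least likely to attend.
- **The exclusion is visible.** SAP 4 and 5.1 already plan population counts by regimen, with disposition percentages based on the number randomised, and there is an analysis-sets listing. A reader could rebuild the all-dosed rate, but the reported rates and intervals would not reflect it.
- **Early intolerance is reported elsewhere.** The Safety Population tables cover adverse events leading to discontinuation, and a Kaplan-Meier plot of early termination is planned.
- **Nothing points to unequal losses.** Both arms receive the same total daily dose, take tablets every 12 hours, and are blinded to regimen. Unequal loss remains possible, but nothing in the documents indicates it.
- **Non-response is an estimand choice.** Loss to follow-up need not reflect the regimen. Moreover, a patient who leaves later can remain a Week 24 responder through LOCF, so the fix does not treat all leavers alike. That is fair, but the later leaver at least has an observed response.

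SAP 8.4.1 says other methods will be explored if discontinuations for adverse events are substantial. That does not answer the point: it names no method or threshold and does not cover loss to follow-up or withdrawn consent.

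The SAP 8.4.1 sentence "Missing baseline values will not be carried forward" might be read as the rule that shuts early leavers out. As worded it concerns missing baselines and does not bear on this issue.

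**Conclusion.** The point holds for the secondary responder rates and the exploratory SALT threshold rates. Each dosed patient without any post-baseline SALT raises that arm's rate by about 1.6 points (14 responders, 30 dosed), or 3.3 points for two. This rests on an assumed 0 to 2 such patients per arm, and the true number may be zero. The regimen difference moves materially only if the losses differ between arms. For one or two patients the movement is small beside a half-width of about 25 points.

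A reader might go further and infer that the study's main comparison is biased in favour of the less tolerable regimen. The documents do not support that. The main comparison is the mean relative change at Week 24. The same exclusion applies there, but a patient with no score has no value to enter, and neither the size nor the direction of any effect can be derived from the documents. This is also an estimation study without formal tests, so no decision rule is affected. The change is worth making because it is cheap and removes a post-randomisation exclusion from rates where its direction is known.

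**What to change.** In SAP 4 and 8.5, specify that tables 14.2.2.2 and 14.2.3.4 and the responder figures (14.2.1.2 and 14.2.1.3) use all randomised patients who received study drug, by randomised regimen. A patient with no post-baseline SALT counts as a non-responder at every visit. State that the SAP 3 rule leaving missing values out of percentages does not apply to these patients. If the sponsor prefers to keep the present responder tables, add this as a supportive analysis.

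Keep the present Efficacy Population for the primary and other mean-change summaries. No new count of excluded patients is needed, since SAP 4 and 5.1 already plan it by regimen.

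The cost is SAP wording before database lock and a changed denominator in two tables and their figures, with no new data. Response rates become slightly lower if any such patients exist, and their denominator may differ from that of the mean-change tables, which a footnote should explain.
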